5 SUMMARY OF STUDY DATA

All continuous variables will be summarized using the following descriptive statistics: n (non-missing sample size), mean, standard deviation, median, maximum and minimum. The frequency and percentages (based on the non-missing sample size) of observed levels will be reported for all categorical measures. In general, all data will be listed, sorted by cohort and subject, and when appropriate by visit within subjects. All summary tables will be structured with a column for each cohort.

5.1 SUBJECT DISPOSITION

A tabulation of subject disposition will be presented by cohort and overall, including the number screened, the number dosed at each level, the number for primary analysis, the number that withdrew prior to completing therapy, and reasons for withdrawal.

5.2 PROTOCOL DEVIATIONS

Major protocol deviations will be determined at the end of the study when all data have been entered into the clinical database. Protocol violations will be listed by patient.

5.3 DEMOGRAPHIC AND BASELINE VARIABLES

Patient distribution across demographic and baseline characteristics will be tabulated and presented by dose group and overall.

The following demographic and baseline characteristics will be evaluated:

- 1) Age (calculated as [date of study entry-date of birth]/365.25)
- 2) Gender
- 3) Ethnicity
- 4) Race
- 5) Physical exam
 - Height
 - Weight
 - BMI
 - Body systems (Normal/Abnormal – clinically significant/Abnormal – not clinically significant/Not Done)
 - General Appearance
 - HEENT
 - Heart and cardiovascular
 - Dermatologic
 - Gastrointestinal
 - Musculoskeletal
 - Lymphatic
 - Neurological
 - Respiratory
- 6) Vital signs
 - Blood pressure
 - Heart rate
 - Respiratory rate

- Temperature
- 7) Baseline medical history – MedDRA coded and tabulated by system organ class and preferred term
- 8) Baseline laboratory assessments

6 PRIMARY ENDPOINT ANALYSES

The primary endpoint will be changes in the level of *B. infantis* from baseline evaluated by quantitative PCR using primers for species and strain.

7 SECONDARY ENDPOINT ANALYSES

Since this is an initial study of the use of PBCLN-005 in a clinical population, it is, by definition, hypothesis-generating. Therefore, all statistical analyses will be descriptive for the evaluation of the data between and within dose groups and the placebo group.

7.1 CHANGES IN STOOL MICROBIOTA

7.1.1 Fecal Microbial Diversity

This will include changes in the diversity, composition, and microbial taxa abundance. Microbial evenness and richness will be evaluated across all cohorts.

7.2 CHANGES IN VIABILITY OF PROTEOBACTERIA AND ENTEROCOCCUS

7.3 CHANGES IN BLOOD PARAMETERS

7.4 EVALUATION OF THE USE OF PROTON PUMP INHIBITORS FOR PROTECTION OF *B. INFANTIS*

8 SAFETY EVALUATION

The safety analyses of exposure, AEs and laboratory parameters will include descriptive statistics and will be summarized separately by dose group and overall. Summaries of AEs will be generated by type (AE or SAE), body system and preferred term, severity, and relationship to study product.

8.1 ADVERSE EVENTS

All reported AEs, will be listed, documenting the course, outcome, severity, and causality to study drug. Verbatim terms on CRFs will be mapped to preferred terms and related system organ class using the Medical Dictionary for Regulatory Activities (MedDRA).

Incidence rates of AEs and the proportion of subjects prematurely withdrawn from the study due to AEs will be shown for all dose groups. Incidence rates will also be displayed based on severity and relationship to study drug. AEs with a relationship of “possibly” or “probably” related will be considered by the Sponsor as “related” to the study drug. Events assessed as “unrelated”, “unlikely” related, or where the relationship was not reported will be considered by the Sponsor as “not related” to the study drug. The incidence of SAEs will be provided for each phase. All incidence rates will be categorized and displayed by system organ class and preferred term.

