histamine H2-receptor antagonist (H2 blocker: Pepcid) to transiently reduce the production of gastric acid prior to *B. infantis* ingestion, some study groups will ingest *B. infantis* without PPI pretreatment. It was initially hypothesized that PPI might be necessary to observe *B. infantis* colonization distal to the acid milieu of the stomach. Preliminary data from the first group of subjects tested suggest that omeprazole may be inhibitory to *B. infantis* colonization and that colonization occurs in the absence of gastric acid suppression. *In vitro* data suggest that the inhibitory effect is not seen with the histamine H2-receptor antagonist famotidine. Therefore, this has resulted in a change to this hypothesis. We now seek to determine if colonization occurs in the presence of an acidic milieu in the stomach, if the apparent inhibitory effect of PPI on colonization is real and if the prediction that the effect will not be seen with famotidine is correct because all target group subjects for future studies are on acid blockers.

We also hypothesize that ingestion of PBCLN-005 along with the *B. infantis* will result in a more marked change in immune markers than was seen in the previous study in healthy adults. We will, therefore, evaluate changes in circulating cytokine and growth factor levels following the ingestion of the IP compared to baseline levels and between dose groups.

Methods

We propose to conduct an unblinded six cohort multi-dose trial using 10 subjects per cohort for a total of 60 healthy adult volunteers ages 18-44 in order to evaluate the effects of the use of HMO Concentrate (PBCLN-005) and *B. infantis* on the human microbiome.

Six separate cohorts of both male and female study subjects will receive some form of the IP. All subjects in Cohort groups 1-4 and 6 will be followed from the day of the first dose of IP (day 1) until 28 days (day 29) after the first dose. Subjects in Cohort 1 will consume *B. infantis* once per day for 7 days. Subjects in Cohort 2-4 and Cohort 6 will consume the IP twice per day for 14 consecutive days. Cohorts 1-4 and Cohort 6 will be followed until the 28th day (day 29) following the first day of the feeding protocol (day 1).

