5. Study subjects randomized to Cohort 5 will undergo two consecutive dosing courses. During the first dosing course, they will consume by mouth HMO investigational product

(IP) twice per day for 14 consecutive days. PPI and *B. infantis* will be taken once per day for 7 consecutive days. On dosing days 1-7 the first dose of HMO will be preceded by one hour and up to two hours by a single dose of PPI to protect the *B. infantis* from the acid milieu of the stomach. The subject will mix HMO and *B. infantis* and ingest at least one hour after taking the PPI. On days 8-14, only HMO product will be consumed (neither the PPI nor *B. infantis* will be taken). Cohort 5 will undergo a second dosing course from days 29-42. For all subjects, the HMO and *B. infantis* will be taken in the same manner as the first dosing course. Note: Prior to Protocol Revision 4, two subjects have already been dosed in Cohort 5. The first four of the remaining subjects yet to be enrolled in this cohort will take an H2 blocker in the same manner as the PPI in the first dosing course. The remaining four subjects enrolled into Cohort 5 will not take any PPI or H2 blocker during the second dosing course.

6. Study subjects randomized to Cohort 6 will consume by mouth HMO investigational product (IP) twice per day for 14 consecutive days and *B. infantis* will be taken once per day for 7 consecutive days. On dosing days 1-7 the subject will mix one dose of HMO and *B. infantis* ingest. On days 8-14, only HMO product will be consumed (the *B. infantis* will not be taken).

Table 1 Dosing cohorts

Cohort	Target HMO Amount (days 1-14)	PPI Cohort 5 Only (Course 1 = Days 1-7)	H2 Blocker Cohort 5 Only (Course 2 = Days 29 – 35)	B. infantis (days 1-7)
1	None	No	N/A	Yes, one sachet
2	18g	No	N/A	None
3	4.5g	No	N/A	Yes, one sachet
4	9g	No	N/A	Yes, one sachet
5 ^A	18g	Yes	Yes (4 subjects) No (4 subjects)	Yes, one sachet
6	18g	No	N/A	Yes, one sachet

^A This group will undergo two dosing courses. One from day 1-14 and one from day 29-42. Four of the subjects in the second course will be assigned a H2 blocker and four of the subjects will not take any PPI or H2 blocker.

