Subjects in Cohort 5 will receive two courses of IP. They will be followed from the day of the first dose of study drug (day 1) until 28 days after the first dose (day 29), and then from the first day of their second course (day 29) until the 28th day following the first dose of that course (day 57). Subjects in that cohort will consume the HMO concentrate twice per day for 14 consecutive days during both courses of IP and will be followed until the 28th day following the first day of the second course of the feeding protocol for a total of 57 days.

Study Population

Each subject must meet all of the indicated inclusion criteria and none of the exclusion criteria noted below.

Inclusion Criteria

- Healthy adults between the ages of 18-44 years (subjects must be 18-44 at the time of consent)
- Willingness to complete study specific questionnaires
- Willingness to complete journal to record IP dosing times
- Willingness to complete all study procedures and clinic visits, and provide required samples
- Able to provide stool samples on specific study days

- Willingness to collect and process stool samples at home and transport stool samples to clinic
- Bristol Stool Score of 1 through 5 at time of screening and on day 1, subjects must verbally confirm that they did not have stool conforming to Bristol Stool Score 6 or 7 during the 7 days prior to dosing.
- Able to store up to 9 days of IP in refrigerator
- Sexually active females of child-bearing potential must agree to use highly effective methods of contraception during heterosexual intercourse throughout the study period and for three days following discontinuation of IP, whichever comes later. Examples of highly effective methods include the use of two forms of contraception with one being an effective barrier method (e.g., a condom and spermicide used together), or have a vasectomised partner. Abstinence is acceptable as a life-style choice. Female subjects who utilize hormonal contraceptives as one of their birth control methods must have used the same method for at least 3 months before study dosing
- Provides informed consent

Exclusion Criteria

- Women who are pregnant or breastfeeding, or intend to become pregnant during the course of this study
- Subjects with allergy to, or other reason for contraindication of the PPIs or H2 blocker* chosen for this study.

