- Changes in viability of proteobacteria and *Enterococcus* will be determined by plating on selective media. These measurements will predictive for success in suppressing pathogenic bacterial relatives in future trials.
- Blood parameters, such as cytokine levels at study days -1, 8, 15 and 2 except for Cohort 5 who will also be evaluated on days 36, 43 and 57.
- Determination of the need for protection of *B. infantis* from stomach acid in order for engraftment of the organism into the gut microbiome to occur.

c) Adverse events will be summarized by severity and relationship to study product. All adverse events will be reported on the study case report form designated for this purpose. Any serious and unexpected adverse event determined by the investigator to be definitely or highly likely causally related with the consumption of IP should be reported immediately (but no later than within 24 hours) to the Sponsor's Medical Monitor.

d) Baseline measures as of study entry

e) IP Feeding Protocol

- f) The dose level of PBCLN-005 consumed will be recorded as well as consumption of *B. infantis*.
- g) Demographics; age, gender, ethnicity and race
- h) Stool changes in subject's stool per Bristol Stool Score
- i) IP taste/ flavor on dosing days using a visual acuity scale

Statistical evaluation

Since this is an initial study of the use of PBCLN-005 in combination with *B. infantis*, it is, by definition, hypothesis-generating. Therefore, all statistical analyses will be descriptive. The various indices reflecting the microbiome will be summarized with appropriate descriptive statistics at each day of collection and compared qualitatively across time and by dose. Other quantitative outcome data collected will be summarized by means/medians and standard deviations/inter-quartile ranges. Graphics such as box plots also will be presented. Safety data (tolerability and adverse events) will be presented in tables with proportions (per subject) by dose and overall.

Schedule of Events Tables**Schedule of Events Table**
Cohort 1

Protocol Number 20-CT-001																			
Schedule of Events For Cohort 1 (Day 0 through Day 29)																			
Events	Cohort 1 Screening	Cohort 1 Dosing Days																Cohort 1 Washout	
	D0 (≤ 90 days prior to D1)	D1	D2	D3	D4	D5 (+1D)	D6	D7	D8 (+2D)	D9	D10	D11	D12	D13	D14	D15 (+2D)	D22 (+2D)	D29 (+2D)	
Clinic visit	X	X							X								X	X	
Final Visit																		X	
Informed consent	X																		

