12 LISTING OF TABLES, LISTINGS, AND FIGURES

TABLES

Number	Table Title
14.1.2	Summary of Demographics and Baseline Characteristics

Statistical Analysis Plan
Prolacta Bioscience Protocol 20-CT-001

14.1.3	Summary of Medical History
14.3.4.1	Summary of Hematology by Dose Group and Visit
14.3.4.2	Summary of Electrolytes/Renal by Dose Group and Visit
14.3.4.3	Summary of Liver Serum Analyses by Dose Group and Visit
14.3.4.4	Summary of Physical Exams by Dose Group and Visit
14.3.4.5	Summary of Vital Signs by Dose Group and Visit
14.3.4.6	Summary of Prior and Concomitant Medications
14.3.1.2	Number and Percentage of Subjects with Adverse Events by Treatment Group, System Organ Class and Preferred Term
14.3.1.4	Number and Percentage of Subjects with Adverse Events by Treatment Group, System Organ Class, Preferred Term and Relationship to Treatment
14.3.1.5	Number and Percentage of Subjects with Adverse Events Resulting in Withdrawal from Treatment by Treatment Group, System Organ Class, and Preferred Term
14.3.1.6	Number and Percentage of Subjects with Adverse Events by Treatment Group, System Organ Class, Preferred Term, and Severity

LISTINGS

Number	Listing Title
16.2.1.1	Subject Eligibility
16.2.2.1	Subject Disposition
16.2.2	Protocol Deviation
16.2.4.1	Demographics
16.2.4.2	Medical History
16.2.4.3	Prior and Concomitant Medications
16.2.7	Adverse Events
16.2.8.1	Laboratory Results - Hematology
16.2.8.2	Laboratory Results – Serum Chemistry
16.2.8.3	Laboratory Results – Urinalysis (Drug Screen)
16.2.8.4	Laboratory Results – Pregnancy Test
16.2.8.5	Vital Signs
16.2.8.6	Physical Exams

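### Cohort 5's adverse event percentage covers two courses to day 57, the other cohorts' one course to day 29, and no common-window or by-course table is planned

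*Combined protocol and SAP*

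**What the plan says.** **How AEs are summarised.** SAP 8.1: "Incidence rates of AEs and the proportion of subjects prematurely withdrawn from the study due to AEs will be shown for all dose groups". SAP 5: "All summary tables will be structured with a column for each cohort". In SAP 12, Tables 14.3.1.2, 14.3.1.4 and 14.3.1.6 are titled "Number and Percentage of Subjects with Adverse Events by Treatment Group", followed by coding, relationship or severity. Table 14.3.1.5 does the same for AEs leading to withdrawal. The protocol's Statistical evaluation section agrees: "Safety data (tolerability and adverse events) will be presented in tables with proportions (per subject) by dose and overall". None of these mentions a dosing course, a time window or person-time.

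**The one period-like statement.** SAP 8.1 adds: "The incidence of SAEs will be provided for each phase". It covers serious events only, *phase* is not defined, and SAP 12 lists no SAE table.

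**How long subjects are observed.** Protocol, Methods: "Cohorts 1-4 and Cohort 6 will be followed until the 28th day (day 29"). Protocol Table 1, footnote on Cohort 5: "This group will undergo two dosing courses. One from day 1-14 and one from day 29-42". Protocol, Study Duration, has Cohort 5 followed "for a total of 57 days".

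**Status of this SAP.** SAP 2 makes safety the focus of this version. The expansion announced there concerns the primary and secondary endpoints.

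**The concern.** A subject percentage counts anyone with at least one event during observation, so it can only grow as observation lengthens. Cohort 5 is observed for about twice as long as the others and is dosed a second time, yet its percentage stands in the same row as theirs. Unless no subject can have a first event after day 29, Cohort 5's expected figure is higher even when the underlying risk is identical.

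The comparison most open to misreading is Cohort 5 against Cohort 6. In Table 1 of both the protocol and the SAP, both cohorts receive 18 g HMO plus *B. infantis* and differ in the first course only by the PPI. Acid suppression is a stated objective, so an excess produced by a second course and 28 more days could be taken for a PPI effect. Any overall column also pools unequal windows. Laboratory values and vital signs are tabulated by visit and do not share the problem.

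**Working it through.** **Inputs from the documents**

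- Cohort size: 10; 6 × 10 = 60, which reproduces the stated total (SAP 4.5).
- Last day: 1 + 28 = day 29 for Cohorts 1–4 and 6; 29 + 28 = day 57 for Cohort 5. Both agree with the protocol.
- AE visits in the schedules of events: days 1, 8, 15 and 29 for the other cohorts (4). For Cohort 5, days 1, 8 and 15, then 29, 36, 43 and 57 (3 + 4 = 7).
- AE rate: none. The only AE evidence is the previous volunteer study of the HMO material alone. It reported no treatment-emergent events, its size is not stated, and it had no *B. infantis*.

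**Assumption.** Let *p* be the risk of at least one AE in 28 days, the same in both cohorts. Values from 1 to 30% are tried.

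**Step 1: risk over 56 days.** At constant hazard, *q* = 1 − (1 − *p*)². For *p* = 0.20, *q* = 1 − 0.80² = 0.36. The excess is *q* − *p* = *p*(1 − *p*), here 0.16.

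**Step 2: what the table would show.** Cohort 5 count ~ Bin(10, *q*) and Cohort 6 count ~ Bin(10, *p*), independent. The last column gives both cohorts Bin(10, *p*).

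| *p* | *q* | Expected subjects, C6 vs C5 | P(C5 > C6) as planned | P(C5 > C6), equal windows |
|---|---|---|---|---|
| 1% | 2.0% | 0.1 vs 0.2 | 0.17 | 0.09 |
| 2% | 4.0% | 0.2 vs 0.4 | 0.28 | 0.15 |
| 5% | 9.8% | 0.5 vs 1.0 | 0.47 | 0.27 |
| 10% | 19% | 1.0 vs 1.9 | 0.60 | 0.34 |
| 20% | 36% | 2.0 vs 3.6 | 0.71 | 0.39 |
| 30% | 51% | 3.0 vs 5.1 | 0.77 | 0.40 |

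**Step 3: rare events.** The chance of at least one affected subject in 10 is 1 − (1 − *p*)¹⁰ over 28 days and 1 − (1 − *p*)²⁰ over 56. At *p* = 1% it rises from 10% to 18%; at 2%, from 18% to 33%. The same holds for AE withdrawals if their risk is of that order.

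**Step 4: weaker effect of the second course,** for *p* = 10/20/30%.

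- Half the hazard in course 2: 1 − (1 − *p*)^1.5 = 15/28/41%. P(C5 > C6) = 0.48/0.57/0.62.
- Events recurring in the same subjects (gamma frailty, variance 1): with *H* = *p*/(1 − *p*), 1 − 1/(1 + 2*H*) = 18/33/46%.
- Correlation ρ between courses within a subject: 1 − [(1 − *p*)² + ρ*p*(1 − *p*)]. At *p* = 20% this gives 31.2, 28.0 and 23.2% for ρ = 0.3, 0.5 and 0.8. The excess disappears only at ρ = 1.

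**Step 5: after the change.** On a common window the expected percentage at equal risk is *p* in every cohort, and the excess of 9, 16 or 21 points (at *p* = 10, 20, 30%) is gone.

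**The case against.** The strongest reply is that nothing formal depends on these percentages. All analyses are descriptive, no test or stopping boundary uses them, and no AE comparison of Cohorts 5 and 6 is announced. Every AE is listed, exposure is summarised by dose group, and the different follow-up is stated openly. This stands as to consequence: no error rate is affected. It does not make the percentages comparable, because exposure is not used as their denominator and the columns are laid side by side.

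Second, *phase* may well mean dosing course, since only Cohort 5 has more than one. Even so, it would cover SAEs only.

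Third, the size is assumed, and the only prior evidence is no events at all. That is fair. At 1–2% Cohort 5 would fail to exceed Cohort 6 with probability 0.83/0.72. The larger figures also assume that all 10 subjects take course 2. If 20% did not (an assumption), the 0.71 at *p* = 20% would fall to 0.66. The size shrinks; the direction does not change.

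Fourth, SAP 8.1 speaks of withdrawal from the study and Table 14.3.1.5 of withdrawal from treatment. These are different measures and should be aligned, but neither is restricted to a common window.

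Fifth, a follow-up label and a single day-limited row might be enough for an abbreviated report. A label alone would warn the reader without supplying comparable figures.

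**Conclusion.** The concern holds. Followed as written, the plan produces AE and AE-withdrawal percentages for Cohort 5 that are not comparable with those of the other cohorts. The direction follows from the design: at equal risk the expected figure is higher whenever a first event after day 29 is possible. The size cannot be fixed from the documents. Under constant hazard the percentage nearly doubles at low risk (1% to 2.0%) and rises by 9 to 21 points at risks of 10–30%. It rises by less if events cluster at first exposure or recur in the same subjects. If AEs are as rare as 1–2%, the table will often show no difference. This is a matter of interpretation in a descriptive safety report. It should be corrected because safety is what this SAP version is for and the correction is cheap.

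**What to change.** In SAP 8.1 and Tables 14.3.1.2, 14.3.1.4, 14.3.1.5 and 14.3.1.6:

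1. Assign each AE, and each withdrawal through the AE that caused it, to course 1 or course 2 by onset date. Footnote any withdrawal that occurs after day 28 from an event that began earlier, and use one withdrawal definition in both places.
2. Compare cohorts on one window: onset from first dose through study day 28 and, in Cohort 5, before the first course-2 dose. Cutting at day 28 avoids the +2-day allowance on day 29.
3. Show Cohort 5 course 2 in its own column, with subjects dosed in that course as denominator. Label whole-study totals with the length of follow-up.
4. Define *phase* for SAEs as the same course 1 / course 2 split.

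Separately, reconcile the documents on acid suppression before showing course-2 AEs by acid-suppression subgroup. SAP Table 1 gives a PPI to Cohorts 1–5, and the SAP's course-2 schedule shows a PPI where applicable. The protocol gives acid suppression to Cohort 5 only, with an H2 blocker for some subjects in course 2. With subgroups of 4, 4 and 2, counts in a listing or footnote are enough.

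**Cost:** one derived period flag from onset and dosing dates, and extra columns in four tables. No new data are needed. AEs starting on or after day 29 in the other cohorts leave the comparison window but stay in the whole-study totals.

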An unconcentrated, pasteurized form of HMO material containing a proportional amount of lactose has already been used in an NIH sponsored clinical trial in premature infants with no reported ill effects.^v Prolacta Bioscience has also completed a healthy volunteer study using the same HMO material as in this trial (with no addition of *B. infantis*) which showed good tolerability. No treatment emergent adverse effects were reported over the course of the trial.^{vi}

The *B. infantis* preparation being used in this trial is a dietary supplement commercially available in the United States and marketed for use in infants. *B. infantis* is characterized as “generally regarded as safe” (GRAS).⁸

Hypothesis

The primary goal of this study is to evaluate the synergy of PBCLN-005 in varying doses with a fixed dose of *B. infantis*, compared with either component of the IP given alone. Synergy is defined as the enhanced gastrointestinal colonization of *B. infantis* upon feeding with HMO feeding. Secondary endpoints will measure changes in the gut microbiome, fecal metabolome and the subject’s immune status as measured by systemic markers. We hypothesize that the combination will result in greater proliferation of *B. infantis* than was seen with the HMO concentrate alone.

Another objective is to understand the role of the low pH of the stomach in colonization of *B. infantis*. For most non-spore forming gut bacteria, the stomach is a barrier to colonization since acid exposure can reduce bacterial titer by 1,000- to 1,000,000-fold. While some subjects in the study will take a proton pump inhibitor (PPI; Zegerid), or a proton pump inhibitor (Zegerid) and

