2 SCOPE OF THE STATISTICAL ANALYSIS PLAN

This version of the Statistical Analysis Plan (SAP) will focus on the safety analyses described in the protocol. These analyses will be included in an initial abbreviated safety report. The details of the analysis of primary and secondary endpoints are included here but will be expanded upon in an amended SAP for the full clinical study report.

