4.7 ANALYSIS POPULATIONS

Since this study is a safety study, the only analytical population will be individuals who receive at least one dose of either active drug or placebo.

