4.8 MISSING DATA

Investigators should make every effort to ensure that loss to follow-up is kept to a minimum and that all data are collected for all subjects at all time points. However, because this is a Phase 1 safety study, no data imputation methods will be used to account for missing data.

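### SAP 8.1 counts adverse events with no causality rating as not related, although SAP 4.8 rules out imputation; if ratings are missing, only the lower bound of the related-AE rate is shown

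*Combined protocol and SAP*

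**What the plan says.** SAP 8.1 (Adverse Events) treats possibly and probably related events as related. Events assessed as unrelated or unlikely are treated as not related, and so are events "where the relationship was not reported will be considered by the Sponsor as" not related. The section also plans AE incidence by relationship, and a listing of all AEs with their causality.

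SAP 4.8 (Missing Data) states that "no data imputation methods will be used to account for missing data". It makes no exception for causality, and neither section refers to the other.

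Three places fix what is counted:

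- SAP 12 lists Table 14.3.1.4 as "Number and Percentage of Subjects with Adverse Events by Treatment Group, System Organ Class, Preferred Term and Relationship to Treatment", so the unit is the subject.
- The protocol, under Statistical evaluation, says: "Safety data (tolerability and adverse events) will be presented in tables with proportions (per subject) by dose and overall".
- SAP 4.7 says that "the only analytical population will be individuals who receive at least one dose of either active drug or placebo".

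SAP 5 adds a general rule: "The frequency and percentages (based on the non-missing sample size) of observed levels will be reported for all categorical measures". Neither SAP 8, SAP 8.1 nor the table list mentions a row for unreported relationship, or a summary that counts unrated events as related.

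**The concern.** Giving a fixed category to a rating that was never made is single-value imputation in effect, and here the value favours the product. SAP 8.1 may be meant as a specific convention, but the SAP does not say so.

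The denominator stays at all dosed subjects, so the rule acts only on the numerator of the related rate and can only leave it unchanged or lower it. The planned table would not show by how much.

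This matters more here than in a later efficacy plan. SAP 2 says: "This version of the Statistical Analysis Plan (SAP) will focus on the safety analyses described in the protocol". It adds that these analyses go into an initial abbreviated safety report. The split by relationship is one of the main displays in that report, and with about ten subjects per cohort a single blank field can separate no related AEs from one.

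**Working it through.** **Inputs from the documents.** Six cohorts of 10 (SAP 4.5): 6 × 10 = 60, which reproduces the stated total. No related-AE rate and no share of missing ratings is given. The counts of 10 and 60 are planned numbers. The protocol allows replacement of subjects, so the number dosed, which is the actual denominator, may be somewhat larger.

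**Bounds, with no assumed rates.** Let

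- n = dosed subjects;
- r = subjects with at least one AE rated possibly or probably related;
- k = other subjects with at least one unrated AE.

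The SAP 8.1 rule reports r/n. Complete ratings could give any value from r/n to (r+k)/n. The hidden width is k/n: 1/10 = 10 points per subject in a cohort, and 1/60 = 1.7 points overall.

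| n | r | k | Reported r/n | Upper bound (r+k)/n |
|---|---|---|---|---|
| 10 | 0 | 1 | 0% | 10% |
| 10 | 2 | 0 | 20% | 20% |
| 10 | 2 | 1 | 20% | 30% |
| 10 | 2 | 2 | 20% | 40% |
| 60 | 0 | 1 | 0% | 1.7% |
| 60 | 2 | 1 | 3.3% | 5.0% |
| 60 | 2 | 2 | 3.3% | 6.7% |

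The values of r and k are illustrations. An unrated AE in a subject already counted as related does not move the overall subject-level rate, though it can move the row for its own preferred term.

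**Denominator check.** If SAP 5 were applied by leaving the k subjects out, the rate would be r/(n−k). For r = 2, k = 2, n = 10 that is 2/8 = 25.0% instead of 20%. Under SAP 8.1, however, every event has a category, so nothing counts as missing and the denominator remains n.

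**How large might it be? Assumed scenarios.** Let p be the true proportion of subjects with a related AE, with one such AE each, and m the share of those AEs left unrated, with subjects independent. The expected downward shift is 100 × p × m points. The chance that at least one subject is moved is 1 − (1 − pm)^n.

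| p | m | Expected shift (points) | Chance, n = 10 | Chance, n = 60 |
|---|---|---|---|---|
| any | 0 | 0 | 0 | 0 |
| 2% | 5% | 0.1 | 1% | 6% |
| 10% | 5% | 0.5 | 5% | 26% |
| 10% | 10% | 1.0 | 10% | 45% |

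The low end is plausible. Of the earlier HMO-only volunteer study the protocol background says: "No treatment emergent adverse effects were reported over the course of the trial".

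**The case against.** The best defence is that SAP 4.8 concerns loss to follow-up and data missing at scheduled time points, while SAP 8.1 is an openly prespecified reporting convention. A specific rule beside a general one is normal drafting, and the recorded rating is not overwritten. That is a fair reading and it softens the inconsistency. It does not change the direction in which the rule moves the related rate.

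Second, every AE is listed with causality (Listing 16.2.7), so in cohorts of ten a reader who finds blank ratings there could count k by hand. This also stands, but the tabulated rate would remain at its minimum.

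Third, SAP 12 gives table titles without shells, so Table 14.3.1.4 might show the raw categories, including unreported. The documents leave this open. The only handling they state is the pooling in SAP 8.1.

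Fourth, the size is unknown, the analyses are descriptive, and no decision or stopping rule uses the split. That limits the point to a minor one. A footnote with the number of unrated AEs would meet part of it, but a count of events does not give the number of subjects k that the upper bound needs.

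**Conclusion.** The concern holds, as a minor point. By a stated rule, SAP 8.1 assigns unrated AEs to the category favourable to the product, and SAP 4.8 rules out imputation without naming this exception. Whenever k is above zero, the planned related-AE rate is the lower end of an undisclosed range of width k/n. In the assumed scenarios the expected shift is 0 to 1.0 point.

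The bounds need no assumption beyond keeping the ratings that were made and using all dosed subjects as the denominator. The expected shifts rest on assumed p and m. The effect is confined to the split by relationship and disappears if every AE is rated.

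**What to change.** 1. In SAP 8.1, stop merging unrated AEs into not related. Give relationship not reported its own row in Table 14.3.1.4, and state that all dosed subjects are the denominator.
2. Add one display that counts unrated AEs as related, labelled as an upper bound, so that r/n and (r+k)/n are both visible and neither is the default.
3. Cross-reference this handling in SAP 4.8.
4. While editing, check that every causality category on the case report form is mapped. SAP 8.1 maps only possibly and probably to related, whereas the protocol's wording on expedited reporting uses stronger levels of causality. The form is not among the documents, so this is a check and not a stated error.

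The cost is one or two sentences, one row and one display, with no new data. The downside is that the upper bound may count some truly unrelated events as related, hence the label. If no ratings are missing, the row is empty and the two displays agree.
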